10.2.3 Adverse event of special interest

An AESI is an adverse event (serious or nonserious) of scientific and medical concern, specific to the IMP or program, for which ongoing monitoring and rapid communication by the Investigator to the Sponsor may be appropriate. Such events may require further investigation in order to characterize and understand them.

For AESIs, the Sponsor must be informed immediately (i.e., within 24 hours), per SAE notification guidelines described in Section 10.3.2, even if not fulfilling a seriousness criterion as an SAE.

The following adverse events are considered AESIs:

- Acute bronchospasm
- Clinically relevant decline in pulmonary function
- Hypersensitivity reactions, including anaphylaxis, which can occur with insulin products, including AFREZZA
- Diabetic ketoacidosis

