		Month 6	Start day of the extension period + 183	[Start day of the extension period +169 , Start day of the extension period + 197]
		Month 9	Start day of the extension period + 274	[Start day of the extension period +260 , Start day of the extension period +288]

Parameter	Study Period	Analysis Visit	Target Relative Day (s)*	Visit Window (Relative Days)*
		Month 12 (Visit 28, EOT)	Start day of the extension period + 365	[Start day of the extension period +351 , Treatment end day of the extension period]
		Follow-up (for Vital Signs only)	Start day of the extension period + 396	[Treatment end day of the extension period + 15, End day of the extension period]

* Start/end day is calculated as the corresponding start/end date – Study Day 1 +1.

- Data will be assigned to analysis visits using the date of measurement and the visit windows (see [Table 2](#) above).
- If multiple measurements are collected within the same visit window, (1) for Screening visit, the last measurement will be used for analyses; (2) for post-baseline visits, the measurement that is closest to the target relative day will be used for analyses. In the event of a tie, the later measurement will be selected for analyses.
- In addition to the analysis visits listed in the table above, a visit of ‘Early Termination’ will also be included, for both the titration period and the extension period. For subjects with early discontinuation, data collected at the Early Termination visit will be summarized and presented at that visit, no matter whether the data has fallen into the visit window of any other visit or not (i.e., for example, if the value from Early Termination visit also falls into the visit window of Week 4, it will be summarized both with the Week 4 data, and with the other data collected at the Early Termination visit). By doing so, special attention can be drawn to the data collected at Early Termination, so if there is any particular safety data pattern associated with early discontinuation, it could be more easily recognized.
- Values which are not collected at Early Termination visits and do not fall into any of the visit windows will not be included in by-visit data summary, but will be presented in subject-listings
- If measurements are taken at multiple scheduled time points on the same day, data will be summarized based on nominal time points. Data collected at unscheduled time points will not be used for analyses.

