8.3.5 Pulmonary Function Testing

Schedule and parameters

Spirometry tests will be performed at screening, visits 2, 9, 15, and 16 in the titration period, visits 19, 22, 25, 28, and 29 in the extension period, as well as at the early termination visits in both periods. At each visit, Forced Expiratory Volume in 1 second (FEV₁) will be collected. At Visit 2, FEV₁ will be collected at several time points: -25 min, 18 min, 55 min, 125 min and 245 min relative to the time of first dose.

Table presentation

FEV₁ value and change from baseline will be summarized descriptively by cohort and analysis visit/nominal time point. For each post-baseline visit/time point, number and percentage of subjects with verified clinically relevant decline in pulmonary function from baseline (as indicated on the eCRF) will be presented by cohort. For percentage calculations, the total number of subjects in each cohort who attend the visit will be used as denominators.

Verified clinically relevant decline in pulmonary function will be captured as AE. A continuous decline will be captured as a single AE. The start date of this event is defined as the date when the criterion of clinically relevant decline (i.e., >15% decrease from baseline) is met for the first time, and the end date of this event is defined as the date when the criterion is no longer met. Each event will be assigned to a study period based on the start date. Duration (in days) of an event will be calculated as end date – start date + 1, and summarized by cohort and study period.

Subject Listings

For spirometry tests, detailed information of every measurement will be listed, by (in the order of) cohort, investigator site, subject and visit/time point.

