9 CHANGES FROM PREVIOUS VERSIONS

REVISION NUMBER	AUTHOR	EFFECTIVE DATE	CHANGES:	REASON:
1.1	[name]	2017/10/20	Remove all description regarding the 2 previous subjects from the Sanofi study.	The 2 subjects will not be included in the any of the analyses
1.1	[name]	2017/10/20	Present PK concentrations/parameters by dose	The PK concentrations and parameters of insulin and FDKP are affected by the dose of AFREZZA®
1.1	[name]	2017/10/20	Change ‘clinically relevant decline’ in pulmonary function to ‘verified clinically relevant decline’, and add a table to summarize the duration of verified clinically relevant decline.	Clinically relevant decline will be verified by the sites. The duration of such decline is of interest
1.1	[name]	2017/10/20	Add a table to present the use of post-meal dose.	It is of interest to see how frequently post-meal (i.e., supplemental) doses need to be given
1.1	[name]	2017/10/20	Adjust visit windows	From clinical point of view, it doesn’t make sense to use very large windows
1.1	[name]	2017/10/20	Add ‘Early Termination’ visit to the by-visit summary tables	To draw special attention to data collected at the early termination visit. If there is some particular data pattern associated with subject discontinuation, it could be more easily recognized.
1.1	[name]	2017/10/20	Create a summary table for ‘documented hypoglycemia’ (defined as glucose < 70 mg/dl), including the subcategories of asymptomatic/symptomatic documented hypoglycemia	This category of hypoglycemia is of interest from medical point of view.
1.1	[name]	2017/10/20	When calculating average dose/SMBG at weekly interval in the titration period and at monthly interval in the extension period, only include data collected in the 2 nd half of the interval (i.e., within 3 days prior to the each clinic visit in the titration period and within 2 weeks prior to each visit in the extension period) in the analysis.	These values are more of interest from clinical point of view.

REVISION NUMBER	AUTHOR	EFFECTIVE DATE	CHANGES:	REASON:
3.0	[name]	2019/12/10	Add the imputation rules of incomplete T1DM diagnosis date for the calculation of duration of T1DM	As analysis needed
3.0	[name]	2019/12/10	Add “Drug-related serious TEAEs” item for TEAE overall summary	To show the number and percentage of subjects who has any drug-related serious TEAEs in the AE overall summary table

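### FEV1 decline is counted only through an undefined site verification on the eCRF, so a measured fall of more than 15% that the site does not verify enters no count table

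*SAP*

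**What the plan says.** **Schedule.** SAP 8.3.5 states: "Spirometry tests will be performed at screening, visits 2, 9, 15, and 16 in the titration period". Early termination visits are added. Visit 2 has one pre-dose test and four post-dose tests.

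**The count.** For each post-baseline visit or time point, the number and percentage of children with "verified clinically relevant decline in pulmonary function from baseline (as indicated on the eCRF) will be presented by cohort". The denominator is the children in the cohort who attend that visit.

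**The criterion.** The 15% figure appears in the next paragraph of 8.3.5, which dates the adverse event: it starts on the date when "the criterion of clinically relevant decline (i.e., >15% decrease from baseline) is met for the first time". The change log in SAP section 9 says "Clinically relevant decline will be verified by the sites", without saying how. Protocol 10.2.3 lists "Clinically relevant decline in pulmonary function" as an adverse event of special interest (AESI), to be notified within 24 hours, and gives no figure.

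**Which values enter by-visit summaries.** Under SAP 8.1.1.2, values that are not from early termination visits and "do not fall into any of the visit windows will not be included in by-visit data summary"; they go to the listings. The bullet on several time points within one day ends: "Data collected at unscheduled time points will not be used for analyses". If a window holds several values, the one closest to the target day is used, and a tie goes to the later one.

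**The concern.** A site's mark decides whether a decline exists, while a numeric rule decides when it began. Nothing in the two documents ties the mark to the measured FEV1, and no table in SAP Appendix 3 counts falls above 15% from the recorded values.

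Protocol 4.4 says safety has not been evaluated in children, and it names acute bronchospasm and FEV1 decline among the matters to watch. Protocol 6.5 and 13.10 have the sponsor and the DMC review safety data before Cohorts 2 and 3 open. Table 14.3.4.2 is in the DMC package. If it shows no declines, the reader cannot tell whether no child fell by more than 15% or no fall was verified.

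**Working it through.** The plan states no figure on this point to reproduce. The check enumerates the FEV1 windows in SAP Table 2, applies the selection rule, and traces where each kind of fall is reported.

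**1. Days without a window, titration.** The windows are Day 1 (nominal time points), Days 8 to 21 (Week 2), Day 22 to treatment end (Week 4), then follow-up. The uncovered days are 2 to 7, which is 6 days. No spirometry is scheduled on them, so only an unscheduled test is affected. An early termination test on those days is kept in its own row.

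**2. Selection inside the Week 2 window (target Day 15).** Days on which another test would replace Visit 9:

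| Visit 9 held on | Days that would replace it |
|---|---|
| Day 14 | 15, 16 (Day 16 ties and is later) |
| Day 15 | none |
| Day 16 | 15 |

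An unscheduled test can therefore enter the window by date, but a scheduled Visit 9 nearly always displaces it, however low the unscheduled value.

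**3. Extension period as the SAP defines it.** Assume treatment ends at start day + 365. The windows are +77 to +105, +169 to +197, +260 to +288 and +351 to +365, so 29 + 29 + 29 + 15 = 102 of 366 days (28%) are covered. An unscheduled test on the other 264 days has no window.

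**4. Where a fall of more than 15% is reported.** I take Table 14.3.4.2 to be the table that 8.3.5 describes. Its title in Appendix 3 omits the word *verified*, and the shells are in a separate file.

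| Fall of more than 15% | Decline count (14.3.4.2) | TEAE, AESI and duration tables | FEV1 means (14.3.4.1) | Spirometry listing |
|---|---|---|---|---|
| Verified, value selected for a visit | yes | yes | yes | yes |
| Verified, value not selected | no | yes | no | yes |
| Not verified, value selected | no | no | yes, inside a mean | yes |
| Not verified, value not selected | no | no | no | yes |

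The adverse event column follows verification because 8.3.5 captures a *verified* decline as an adverse event. A related event, such as bronchospasm, could still be reported on its own account.

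**5. Weight of one child.** With all planned children attending: 100/14 = 7.1 percentage points in Cohorts 2 and 3, and 100/18 = 5.6 in Cohort 1.

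**The case against.** The strongest reply is that the plan already has an any-time count. A verified decline becomes an adverse event whose start is not tied to a window, and the AESI table (14.3.1.11) gives numbers and percentages of children by cohort and period. The DMC also receives the TEAE table (14.3.1.2), the TEAE listing (16.2.7.2) and every spirometry result (16.2.8.3). Protocol 13.8 makes review of individual values part of the safety evaluation. Site verification and tighter windows were deliberate changes with reasons in the log, and poor efforts are a fair worry in young children.

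Most of this stands, and it defeats several stronger readings:

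- *Only scheduled visits count.* Not so. Early termination values are always summarised, and values are assigned to windows by date.
- *All unscheduled spirometry is barred from analysis.* The sentence sits in a bullet about time points within one day. Its reach to unscheduled visits is unclear.
- *A decline that is not re-tested stays unverified, or sites mark by judgement alone.* Neither document equates verification with re-testing, and the eCRF, which may carry the 15% figure, is not available here.
- *The falls that matter most go missing.* The scheduled Day 1 post-dose tests at 18, 55, 125 and 245 minutes and the early termination tests remain in the table, and neither document schedules symptom-triggered spirometry.
- *About a fifth of titration is lost (6/28 = 21%).* No test is planned on those six days.
- *Two of 14 children could fall and the summaries show none.* If the sites verified both falls, the AESI table would show both.

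The reply does not reach the last two rows of the routing table. The adverse event route passes through the same verification, so it cannot recover an unverified fall. The AESI tables, the duration table (14.3.4.3) and the AESI listing are not marked for the DMC. A reader seeking unverified falls must work them out by hand from the listing.

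**Conclusion.** The concern holds in a limited form. Table 14.3.4.2 counts a site-verified mark by visit, not the measured FEV1. For verified declines the window and selection rules matter little, because the adverse event tables pick those declines up at any time. For unverified falls above 15% no count exists: they appear only in the listing, or inside an FEV1 mean if the value is selected for a visit.

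The documents give no basis for estimating how many such falls will occur. Each would be worth 7.1 or 5.6 percentage points at the planned cohort sizes. The conclusion assumes that sites may leave some measured falls above 15% unverified, and that the separate table shells add no derived count. If the eCRF sets the mark automatically from the 15% rule, the gap largely closes, but the SAP should then say so.

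**What to change.** In SAP 8.3.5, add one derived row to Table 14.3.4.2, by cohort and study period: the number and percentage of children with any post-dose FEV1 more than 15% below baseline. Compute it from all recorded spirometry (scheduled, unscheduled, out of window and early termination). The denominator is safety-population children with at least one post-dose FEV1. Exempt this row from the exclusion and closest-to-target rules in 8.1.1.2, and keep the site-verified count beside it.

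In the same edit, define *verified* in 8.3.5 and state in 8.1.1.2 whether the sentence on unscheduled time points covers unscheduled visits.

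Separately, the sponsor should reconcile protocol 10.2.3, which has no threshold, with the SAP's "i.e., >15% decrease from baseline". If that changes the figure, the derived row should follow it.

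The cost is one row and a few sentences, with no new procedure or data. The downside is small: some low values will be poor efforts, which is why the verified count stays. The table is already in the DMC package, so the row reaches the DMC without a further change.

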7.3 EXCLUSION CRITERIA

Subjects who have met all the above inclusion criteria listed in Section 7.2 will be screened for the following exclusion criteria:

1. Body mass index below 25th or above 95th percentile for age and gender according to Centers for Disease Control and Prevention growth charts
https://www.cdc.gov/growthcharts/html_charts/bmiagerev.htm
2. History of physician diagnosis of asthma or any other clinically important pulmonary disease, or use of any medications to treat such conditions within the last year;
3. Allergy or known hypersensitivity to AFREZZA® or to drugs with similar chemical structure;
4. Unstable diabetes control, defined as 2 or more episodes of severe hypoglycemia (i.e., an episode associated with a seizure, coma, or loss of consciousness) or any hospitalization or emergency room visit for poor diabetes control, ketoacidosis, hypoglycemia, or hyperglycemia within the preceding 3 months from screening;
5. Serum creatinine \geq the upper limit of normal for age;
6. Respiratory tract infection within 30 days before screening or between screening and initiation of treatment period; subject may return 4 weeks after resolution of the infection for rescreening;
7. Evidence of any complication of diabetes (proliferative retinopathy, autonomic neuropathy, nephropathy, etc), or likelihood of requiring laser photocoagulation, vitrectomy, or other specific treatment for diabetic retinopathy in the coming year;
8. Smoking of tobacco or other substances or positive urine cotinine testing (>100 ng/mL);
9. Positive urine drug screen;
10. Positive urine pregnancy test for female subjects of childbearing potential;
11. Inability to perform study procedures including pulmonary function testing;
12. Exposure to any investigational product(s) in the past 3 months or 5 half-lives, whichever is more;
13. History of eating disorder;
14. Any disease or exposure to any medication which, in the judgment of the principal

Investigator, may impact glucose metabolism;

15. Any concurrent medical or major psychiatric condition that makes the subject unsuitable for the clinical study or impairs the subject's ability to participate in the study.

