9.2.4 Safety assessment during the study

Safety assessments during the study will be done according to the Flow Chart 1.1 and will include, but is not limited to:

- Physical examination: the abbreviated physical examinations will include, but not limited to, general appearance, mental status, respiratory and cardiovascular systems, and other evaluations deemed appropriate by the Investigator for safety reasons
- Body weight (kg)
- Vital signs (respiratory rate, sitting blood pressure, and pulse measurements) will be recorded after the subject has been sitting for 5 minutes
- Laboratory tests:
 - Urine pregnancy test: females of childbearing potential
 - Urine cotinine
- Adverse events spontaneously reported by the subject or observed by the Investigator will be monitored
- FEV₁ testing: Spirometry will be done to assess pulmonary function. Another pulmonary function test may be done after the consultation of a pediatric pulmonologist if the subject is unable to perform spirometry
- Concomitant medications reported by the subject or by the Investigator will be recorded

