12.1.3.4 End of titration (Visit 15)

Subjects will return to the site 3 ± 1 days after the last telephone contact at Visit 14. During this visit (Visit 15), FEV₁ will be assessed, and post-dose SMBG values since the last visit and current AFREZZA® doses will be reviewed. Subjects will be discharged from the clinic after an abbreviated physical examination (evaluating general appearance, mental status, respiratory and cardiovascular systems, and any other evaluations deemed necessary by Investigator).

Subjects will be assessed according to the Flow Chart [1.1](#). Assessments include but are not limited to the following:

- Urine pregnancy test for females of childbearing potential
- HbA1c
- Urine cotinine
- Anti-insulin antibody
- Review of concomitant medications and AEs
- Abbreviated physical examination (general appearance, mental status, respiratory and cardiovascular systems, and other evaluations deemed appropriate by the Investigator for safety reasons)
- Body weight
- Vital sign measurements
- Blood glucose via glucose meter reading
- Spirometry or another pulmonary function test for a subject who is unable to perform the spirometry test
- 7-point glucose data will be reviewed
- Subjects will return all study supplies and receive a prescription for usual prandial RAA and for basal insulin

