8 STATISTICAL METHODS

8.1 General Considerations

In this study, unless otherwise specified, all analyses will be performed in a descriptive manner by age cohort (including ‘Cohort 1’, ‘Cohort 2’, ‘Cohort 3’ and ‘Total’). The ‘Total’ group will include all subjects in the analysis population.

Where appropriate, all dimensions will be summarized in metric units, but listings will, in addition, represent values as collected.

For continuous variables, the number of subjects, mean, standard deviation, median, minimum, and maximum values will be displayed, as appropriate according to the type of data. The minimum and maximum will be displayed to the same number of decimal places that the data were recorded to. The mean and median will have 1 extra decimal place and the standard deviation will have 2 extra decimal places. The geometric mean and coefficient of variation (CV) will have 2 extra decimal places. Confidence interval (of the mean) will have the same decimal precisions as the mean.

For categorical variables, frequency counts and percentages of total for each category will be presented; missing values will be treated as a separate category, where appropriate. Percentage will be presented in 1 decimal place.

Visit specific data (e.g., 7-point SMBG or pulmonary function tests) will be summarized by analysis visit, which is defined based on the visit windows specified in Section 0

Non-visit specific data (e.g., hypoglycemic events or daily dose) will be summarized by study period and/or by time interval. See relevant sections for more details.

8.1.1 **Data Handling/Imputation Methods**

8.1.1.1 **Missing Data Imputation**

Unless otherwise specified, missing data other than start date of adverse events (AE) or start/end date of concomitant medications (CM) will not be imputed.

The imputation rules for start date of Aes and start/end date of CMs are as follows:

Adverse Events

- Start date
 - If the start date is completely missing, the start date is set to the date of first dose.
 - If the year is present and the month and day are missing or the year and day are present and the month is missing:

If year = year of first dose, then set month and day to month and day of first dose

Version Date: 17-Jan-2020

- If year < year of first dose, then set month and day to December 31.
- If year > year of first dose, then set month and day to January 1st.
- If the month and year are present and the day is missing:
 - If year = year of first dose and

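### The percentage with clinically relevant decline in pulmonary function is taken over all visit attendees, so an attendee without an evaluable result counts as no decline and the percentage may be understated

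*SAP*

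**What the plan says.** SAP 8.3.5 counts, by cohort and for every post-baseline visit and time point, the subjects flagged on the eCRF with a verified decline in pulmonary function. For the percentages, "the total number of subjects in each cohort who attend the visit will be used as denominators". The same section gives the criterion as "i.e., >15% decrease from baseline". At Visit 2, FEV1 is read once before the dose and four times after it (18, 55, 125 and 245 minutes).

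The protocol foresees on-study subjects who cannot do the test. Section 9.2.4 says: "Another pulmonary function test may be done after the consultation of a pediatric pulmonologist if the subject is unable to perform spirometry". The Visit 15 procedures (12.1.3.4) list "Spirometry or another pulmonary function test for a subject who is unable to perform the spirometry test", and the Visit 16 procedures (12.1.3.5) repeat this.

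Two provisions narrow the problem. Exclusion criterion 11 removes subjects with "Inability to perform study procedures including pulmonary function testing". Inclusion criteria 10 and 11 require FEV1 and forced vital capacity of at least 70% of predicted.

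On missing values, SAP 8.1 says that, unless otherwise specified, "missing data other than start date of adverse events (AE) or start/end date of concomitant medications (CM) will not be imputed". For categorical variables, "missing values will be treated as a separate category, where appropriate".

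**The concern.** A percentage fall from baseline can be judged only when there is a usable value at both ends. An attendee with no evaluable result adds one to the denominator and has no measurement that could add to the numerator. In the table that subject looks the same as one who was measured and found stable. The distortion can go only one way, towards apparent safety.

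Clinically relevant decline in pulmonary function is an adverse event of special interest in both documents. SAP Appendix 3 marks the decline table (14.3.4.2) for the DMC package, and SAP Section 7 describes a rolling review by the sponsor and the DMC that allows enrollment into Cohorts 2 and 3. Cohorts of 14 to 18 are small enough for one or two subjects to move a percentage visibly.

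**Working it through.** **The plan's own figures.** The documents state no expected decline rate and no expected rate of missing spirometry, so there is no figure on this point to reproduce. The only computable design figure is the precision table for CL/F. Using 1 - exp(-t(0.975, n-1) × SD × sqrt(chi2(0.80, n-1)/(n-1)) / sqrt(n)), all 25 cells reproduce to one decimal, including 38.0% at n = 14 and SD 0.725. That table bears on this point only through the cohort sizes.

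**Inputs.**
- N, attendees in a cohort: at most 18, 14 and 14 (SAP 3.2), or 46 in the Total column. Full attendance is assumed.
- x, subjects with a verified decline: not in the documents; assumed 1 or 2.
- m, attendees without an evaluable result: not in the documents; assumed 0 to 3.

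**Formulas.** Planned percentage = x/N. Percentage among evaluable subjects = x/(N - m). Their ratio, planned over evaluable, is (N - m)/N.

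| N | m | x | Planned x/N | Evaluable x/(N - m) | Difference (points) | (N - m)/N |
|---|---|---|---|---|---|---|
| 14 | 0 | 1 | 7.1% | 7.1% | 0.0 | 1.000 |
| 14 | 1 | 1 | 7.1% | 7.7% | 0.5 | 0.929 |
| 14 | 1 | 2 | 14.3% | 15.4% | 1.1 | 0.929 |
| 14 | 3 | 1 | 7.1% | 9.1% | 1.9 | 0.786 |
| 14 | 3 | 2 | 14.3% | 18.2% | 3.9 | 0.786 |
| 18 | 1 | 1 | 5.6% | 5.9% | 0.3 | 0.944 |
| 18 | 3 | 1 | 5.6% | 6.7% | 1.1 | 0.833 |
| 18 | 3 | 2 | 11.1% | 13.3% | 2.2 | 0.833 |
| 46 | 3 | 1 | 2.2% | 2.3% | 0.2 | 0.935 |

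Differences are taken before rounding. With x = 0 both percentages are zero whatever m is.

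**Where m can arise.** First, a subject who cannot perform spirometry at a visit, with the alternative test either not done (9.2.4 makes it optional) or not countable. Second, Visit 2: the percentage is reported per time point but the denominator is defined by visit. Anyone present that day is in the denominator at all four post-dose times, including any time at which the reading was missed or unusable.

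**Comparison within the SAP.** The anti-insulin antibody table (8.3.10) carries a category for tests not done, and the ECG table (8.3.8) shows missing values as their own category. Section 8.3.5 specifies neither.

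**The case against.** The case on the other side has several parts.

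- **Inability is a contingency.** Subjects are screened for the ability to do the test, and SAP 8.3.5 plans an FEV1 collection at each spirometry visit. This stands. A reader might infer that the protocol expects a group of attendees without FEV1, or that the rate is in fact understated. The documents support neither: they give no number for m or x, and both must be at least 1 for any effect.
- **An alternative test might be counted.** The numerator is an eCRF flag for decline in pulmonary function, and the criterion does not name FEV1. A reader might infer that a subject given another test can never be flagged. The SAP does not say so. This also stands, and it shapes the remedy: if such a decline can be flagged, an FEV1-only denominator would omit a subject who is in the numerator.
- **The information is available elsewhere.** The FEV1 summary (Table 14.3.4.1), whose standard statistics include the number of subjects, and the spirometry listing (16.2.8.3) also go to the DMC. A careful reader could recover the evaluable count. This limits the harm but leaves the percentage in the decline table as specified.
- **A missing category may be shown anyway.** The general rule applies only where appropriate and does not alter the explicit denominator in 8.3.5. The table shells are in separate files, so a missing row cannot be ruled out.
- **Attendance could be programmed as having an FEV1 in the window.** SAP Table 2 does assign data by measurement date, but that reading departs from the words of 8.3.5.
- **The differences are small against sampling error.** The exact 95% interval for 1/14 is 0.2% to 33.9%. This is true, but imprecision does not excuse a denominator that can bias in one direction only.

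**Conclusion.** The point holds in conditional form. As written, the rule counts an attendee without an evaluable result as having no decline, and the percentage may then be understated by the factor (N - m)/N. With N = 14 and one decline, that is 7.1% versus 7.7% for one unevaluable attendee and 7.1% versus 9.1% for three. Both values of m are assumptions, and the entry criteria favour the smaller. In the Total column the effect is close to nil (2.2% versus 2.3% for three).

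No hypothesis test, sample size or numerical stopping threshold uses this percentage. The change is still worth making: this is a stated rule on a DMC table for an event of special interest, and its only possible error is towards reassurance.

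**What to change.** In SAP 8.3.5, define the denominator as subjects in the cohort with an evaluable baseline and an evaluable result at that visit or, for Visit 2, at that time point. Beside it, show the number attending but not evaluable. State whether a result from an alternative pulmonary function test counts towards the decline criterion, and apply the same answer to numerator and denominator.

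The count should be shown because dropping unevaluable subjects does not remove all doubt: they may be missing for respiratory reasons. With N = 14, one decline and m = 3 (assumed), counting all three as declines would give (1 + 3)/14 = 28.6%. A reader who sees m can judge that range.

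The cost is about a sentence of SAP text and one table column, with no new visits or procedures.
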